1.4 Correlative/Exploratory Objectives for Enrolled Participants

- 1.4.1 To explore tissue biomarkers of antitumoral immune activity and tumor genomic instability as predictors of response and resistance to sacituzumab govitecan plus pembrolizumab compared to sacituzumab govitecan alone in patients with HR+ / HER2- MBC.
- To characterize baseline Trop-2 expression by histological assessment and correlate with disease response to treatment (PFS, ORR by RECIST 1.1, OS).
 - To assess changes in Trop-2 staining, from baseline to on-treatment and at-progression, and correlate with disease response to treatment (PFS, ORR by RECIST 1.1, OS).

- To characterize tumor-infiltrating lymphocytes (TILs), by histological assessment, at baseline and correlate with disease response to treatment (PFS, ORR by RECIST 1.1, OS).
 - To characterize the expression of markers of immune cell subsets (i.e., CD8 for cytotoxic T cells, CD68 for macrophages), inhibitory checkpoint pathway molecules (i.e., PD-1, PD-L1, TIM3, LAG3), and co-stimulatory pathway molecules (i.e., GITR, OX40) by immunohistochemistry (IHC) and/or immunofluorescence (IF).
 - To explore whether immunosuppressive and/or immune-stimulating immune marker profiles at baseline correlate with disease response to treatment (PFS, ORR by RECIST 1.1, OS).
 - To characterize mutational load and neoantigen burden at baseline and correlate with disease response to treatment (PFS, ORR by RECIST 1.1, and OS).
 - To characterize RNA expression signatures of immune pathway activation and DNA damage repair deficiency at baseline and correlate with disease response to treatment (PFS, ORR by RECIST 1.1, and OS).
 - To explore whether changes in TILs, immunosuppressive and/or immune-stimulating immune marker profiles, mutational load, neoantigen burden, and RNA expression signatures, between paired biopsies from baseline and after 2 cycles of treatment, correlate with disease response to treatment (PFS, ORR by RECIST 1.1, OS).
 - To explore mechanisms of resistance to sacituzumab govitecan plus pembrolizumab compared to sacituzumab govitecan alone in paired biopsies from baseline and at time of progression.
 - To explore whether the number and/or type of mutations identified using a next generation sequencing (NGS) panel is correlated with patient outcomes (PFS, ORR by RECIST 1.1, and OS). This will be performed on DFCI participants only.

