For a subset of patients who are enrolled at DFCI, single-nucleus RNA sequencing will be performed on biopsies at baseline, on treatment, and, when available, on progression. These studies will determine whether changes in RNA expression signatures specific to tumor and immune cells correlate with treatment response and resistance. These analyses will also investigate whether particular immune cell subsets are enriched in responders compared to non-responders, as suggested by studies in other tumors treated with checkpoint inhibitors. Additional single-cell techniques may be added to the single-cell RNA sequencing, such as cellular indexing of transcriptomes and epitopes by sequencing (CITE-seq), a method that quantifies cell-surface proteins at a single-cell level.⁹⁴

Assay 4: Whole Exome, Whole Genome Sequencing, DNA Methylation

All DNA sequencing will be performed at the Broad Institute; this may include SNP-arrays for germline genomic analyses, as well as exome and/or whole genome sequencing. Tumor biopsy specimens may be assessed using the most current and informative methodologies at the time that correlative science is performed. Potential assays that may be performed on frozen or FFPE metastatic samples and/or FFPE primary samples include:

- Whole Genome sequencing depth of $\geq 40X$ coverage, or Whole Exome sequencing depth of $\geq 500X$ coverage.
- AFFY SNP 6.0, or Illumina SNP arrays for genotypes and DNA copy number changes may be performed.
- DNA methylation: Illumina Infinium 450K methylation arrays.

Previously performed, CLIA-approved NGS panels (i.e., DFCI's Oncopanel) on participants (either from the pre-screening population or the enrolled population) may be requested and utilized in these analyses.

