Optional repeat biopsies will be performed at time of progression to explore changes in TILs and other tissue markers. Descriptive statistics will be used to summarize the change in TILs, and inferences on treatment-effects will use non-parametric tests (e.g., Wilcoxon rank sum) with two-sided alpha 0.05. The association of changes in TILs with clinical outcomes of PFS and OS will be exploratory and hypothesis generating in the subset of patients with evaluable repeat biopsies. Analysis plans will consider using Cox models with time-varying covariates to account for the post-baseline assessments.

C) For secondary correlative endpoints to characterize the expression of tumor markers by immunohistochemistry (IHC) and/or immunofluorescence (IF), descriptive statistics and agglomerative hierarchical clustering techniques will be used to summarize the distribution and patterns of profiles observed in baseline samples. Tests of association with clinical outcomes (PFS, OS, ORR) will be exploratory using Cox proportional hazard and logistic regression models, and inferences will use the Benjamini-Hochberg method to control the false discovery rate. Any positive findings will require validation in future studies with independent samples for unbiased estimates of the association with treatment effects and clinical outcomes.

Efficacy endpoints will be analyzed according to Trop-2 expression, which will be evaluated as percent of positive cells, intensity, a composite score, or another method. Analyses of Trop-2 expression are descriptive and exploratory in nature and intended to examine the distribution of Trop-2 expression levels at different biopsy sites and assess associations between Trop-2 expression and efficacy outcomes, such as PFS, OS and ORR, for which separate analyses will be performed according to Trop-2 expression (above and below median) and treatment group.

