D) Single-cell RNA sequencing will be performed on biopsies at baseline, on treatment, and, when available, at progression for a subset of patients enrolled at DFCI to assess the relationship of timepoint-specific tumor and immune cell subpopulations with clinical outcomes in exploratory analyses. In addition, changes in single-cell RNA expression signatures across these timepoints will be correlated with response. Standard preprocessing and quality control algorithms will be performed to filter out low quality cells and to normalize the expression data. Differentially expressed genes will be identified using the Benjamini-Hochberg procedure to control the false discovery rate for multiple comparisons. Descriptive statistics and clustering techniques, including principal component analysis and t-distributed stochastic neighbor embedding, will be employed to summarize the distributions of the expression data and identify tumor and immune cell subpopulations. Changes in cell subpopulations between baseline, on-treatment, and at progression biopsies will be assessed with Wilcoxon signed-rank tests, while differences in cell subpopulations between responders and non-responders will be compared with Mann-Whitney tests. Preliminary associations of tumor and immune cell subpopulations with progression-free and overall survival will be explored using Cox proportional hazard models.

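### The single-cell analyses in section 13.7.1 D never use treatment arm, so they do not estimate what pembrolizumab adds, although objective 1.4.1 is comparative

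*Combined protocol and SAP*

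**What the plan says.** Section 13.7.1 D covers single-cell RNA sequencing at baseline, on treatment and, where a sample exists, at progression, "for a subset of patients enrolled at DFCI". It lists four analyses of outcome or change:

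- Change over time: "Changes in cell subpopulations between baseline, on-treatment, and at progression biopsies will be assessed with Wilcoxon signed-rank tests".
- Response groups: "differences in cell subpopulations between responders and non-responders will be compared with Mann-Whitney tests".
- Signature change: "changes in single-cell RNA expression signatures across these timepoints will be correlated with response".
- Survival: "Preliminary associations of tumor and immune cell subpopulations with progression-free and overall survival will be explored using Cox proportional hazard models".

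None names treatment arm as a grouping, covariate or interaction. Section 9.3.3 (Assay 3) describes the assay in the same terms, asking whether "particular immune cell subsets are enriched in responders compared to non-responders, as suggested by studies in other tumors treated with checkpoint inhibitors".

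One of the objectives under 1.4.1 is "To explore mechanisms of resistance to sacituzumab govitecan plus pembrolizumab compared to sacituzumab govitecan alone in paired biopsies from baseline and at time of progression", and the heading of 1.4.1 carries the same comparison. Section 9.2.1 says the single-cell work is meant to find signatures of response and resistance to immunotherapy, which only Arm A receives.

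Elsewhere section 13.7.1 does use arm. Part A has a treatment covariate and an interaction test for baseline TILs. Part B has an Arm A versus Arm B rank-based test of TIL change. The paragraph on progression biopsies says that "inferences on treatment-effects will use non-parametric tests (e.g., Wilcoxon rank sum) with two-sided alpha 0.05", in a sentence about TILs. Part C analyses Trop-2 by treatment group.

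**The concern.** Both arms receive sacituzumab govitecan. Section 2.5 reports that irinotecan, whose active metabolite is its payload, depletes regulatory T cells and raises MHC class I and PD-L1 expression in murine models. It hypothesises that sacituzumab govitecan will itself enhance T-cell infiltration. Section 13.7.1 B builds this in by assuming a TIL rise of 4.2 points in Arm B. A before-after shift in immune cell subsets is therefore expected without pembrolizumab.

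A signed-rank test on that shift answers whether something changed on treatment. It does not answer whether adding pembrolizumab changed it further. Comparing responders with non-responders, or fitting survival models without arm, does not answer that either. At stake is an exploratory aim: the randomised comparison at the early on-treatment biopsy is available from samples already planned, but the plan does not ask for it.

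**Working it through.** **Text check.** No sample size, alpha or power is stated for the single-cell analysis, so there is no figure of its own to reproduce. Sections 1.4, 9, 9.2.1, 9.3.3 and 13.7.1 contain no clear between-arm comparison for it. The progression paragraph in 13.7.1 mentions other tissue markers, but its sentence on treatment effects follows a summary of TIL change and does not clearly reach single-cell data.

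**Inputs for an illustration.** These are borrowed from the TIL plan in 13.7.1 B: mean change 10.4 in Arm A and 4.2 in Arm B, SD 8, 24 pairs per arm.

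**The plan's own TIL figures first.**

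- Within arm, one-sided 0.05: Φ(4.2/8 × √24 − 1.645) = Φ(2.572 − 1.645) = Φ(0.927) = 0.823. This matches the stated 82%; the exact paired t gives 0.802.
- Between arms, difference 10.4 − 4.2 = 6.2, one-sided 0.05: simulation under normality gives 0.821. A noncentral t with the conservative rank-test efficiency of 0.864 gives 0.790. The stated 80% is reproduced.

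**Illustration for the single-cell tests.** Per-patient changes are normal with SD 8, tests are two-sided at 0.05, and there are 4,000 runs per setting. The pairs per arm are assumed. Where two values appear, they come from two independent simulations.

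| Pairs per arm | Signed-rank, Arm A alone, both arms +4.2 | Signed-rank, arms pooled, both arms +4.2 | Rank-sum between arms, both arms +4.2 | Rank-sum between arms, +10.4 vs +4.2 |
|---|---|---|---|---|
| 8 | 21-22% | 46-47% | 3-5% | 24-30% |
| 12 | 34-35% | 68% | 4% | 41% |
| 24 | 66% | 93-95% | 5% | 72-73% |

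The spread at 8 pairs in the last two columns comes from the p-value method. A repeat run gave 29% power with exact p-values and 25% with the continuity-corrected normal approximation.

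**How to read the table.** In the first three result columns pembrolizumab does nothing. The signed-rank columns show power to detect a real change that both arms share. They are not error rates. The rank-sum column stays near its nominal 5% because the shared change cancels.

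**Precision.** Treating the estimate as a difference in means, the 95% half-width is about 1.96 × 8 × √(2/n). That is 7.8 points at n = 8, 6.4 at n = 12 and 4.5 at n = 24, against an assumed difference of 6.2.

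**The case against.** The strongest reply is that section D does what it sets out to do. Its stated purpose is to relate cell subpopulations to clinical outcome, and another item under 1.4.1 asks only whether changes in RNA signatures after two cycles correlate with response. The resistance item does not name single-cell data. Section 9 declares all biomarker analyses exploratory, and section 9.7 lets them be altered when they are performed. All of this stands and limits the weight of the point. It does not supply the missing contrast: the heading of 1.4.1 is comparative, and section 9.2.1 assigns the single-cell work to immunotherapy response and resistance.

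A second reply is that the signed-rank tests may be run by arm, as 13.7.1 B does for TILs. The text does not say. Separate tests would help as description, but a significant result in one arm and not in the other is not a test of the difference.

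A third reply concerns the progression biopsy. It is optional and comes only from patients who have progressed, at differing times on treatment. A between-arm comparison there involves patients selected after randomisation and is not a clean randomised contrast. This is right, and the fix is limited accordingly.

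A reader might also infer that the plan would credit pembrolizumab with a change due to sacituzumab govitecan. The documents do not support that. Section D makes no such attribution, and the checkpoint-inhibitor remark in 9.3.3 concerns responder enrichment, not before-after change.

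**Conclusion.** The point holds as a low-cost improvement. The analyses listed in 13.7.1 D do not use treatment arm and therefore do not estimate what pembrolizumab adds to single-cell changes. No trial decision depends on this.

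Two stronger readings are tempting and should be resisted. One is that the signed-rank percentages, roughly 21% to 95%, are false-positive rates. They are power to detect a true shared change, and the higher set also assumes pooling, which the plan does not state. The other is that the two drugs' effects cannot be separated at all. That is a limit of the listed tests, not of the data: 1:1 randomisation with paired biopsies required in both arms, where tumor is safely accessible, permits the comparison.

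The figures rest on TIL assumptions carried over to a different assay, on normal changes, and on assumed subset sizes. The value of 24 pairs per arm is the plan's TIL figure and is probably optimistic for a single-institution subset. The between-arm comparison also relies on the subset being chosen without regard to arm, which the plan should state.

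**What to change.** In 13.7.1 D:

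1. For the 3-6 week biopsy, compute each patient's on-treatment minus baseline change in each cell subpopulation. Compare Arm A with Arm B by the Wilcoxon rank-sum test already used for TILs, with a Hodges-Lehmann difference and 95% confidence interval. Extend the Benjamini-Hochberg control already named in section D to this family, and label the result exploratory.
2. Report the signed-rank tests separately by arm, as description, and state that they are not evidence of a pembrolizumab effect.
3. Report progression-minus-baseline change by arm descriptively only, giving the reason.
4. State the expected number of pairs per arm and how the subset is chosen.

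This costs a few sentences and a little more analysis, with no new samples. The downside is wide intervals: about 30-40% power at 8 to 12 pairs per arm in the illustration, and less after multiplicity adjustment. The estimate and its interval should therefore lead the report, and a non-significant result should not be read as absence of effect.

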13.7.2 Immunogenomic analysis

Tumor and matched germline blood sequencing data will be processed with standard quality control methods, for instance, excluding samples with poor sequencing coverage and low estimated purity as previously described.¹⁰⁴ We will use established whole exome sequencing (WES) pipelines to determine single nucleotide variants, small insertions/deletions, and larger structural variants with computational filtering of artifacts introduced by FFPE-based DNA extraction and DNA oxidation during sequencing.^{104,105} We will limit our search to highly deleterious variants, specifically known hotspot or putative truncating mutations, such as frameshift insertions/deletions, nonsense mutations, and splice-site alterations. Additional standard analysis methods will be used to assess tumor purity and ploidy, copy number alterations, and mutational clonality, the latter to distinguish genomic alterations more likely to be founder mutations from those more likely to have been acquired with evolution or recurrence.^{104,106} Established analysis procedures will likewise be applied to RNA sequencing (RNAseq) data to estimate transcript abundances, differential gene expression, and significantly enriched pathways.¹⁰⁷ The association of response with genomic alterations, both individual genes and genes combined in pathways, will be reported by contingency tables and tested for significance using Fisher's exact test. The false discovery rate will be controlled with the Benjamini-Hochberg method.

We will compare genomic and transcriptomic markers between responders and non-responders in both an unbiased analysis and a directed assessment of immune mechanisms, including antigen presentation, interferon- γ signaling, T-cell effector pathways, and mutational signatures.¹⁰⁷⁻¹⁰⁹ In addition, we will investigate antigen presentation genes, such as MHC class I genes (*HLA-A*, *HLA-B*, *HLA-C*, *B2M*), MHC class II genes (*HLA-DMA/B*, *HLA-DOA/B*, *HLA-DPA1/B1*, *HLA-DQA1/2*, *HLA-DQB1/2*, *HLA-DRA*, *HLA-DRB1/3/4/5*), master regulators of these two families of genes (*NLRC5* and *CIITA*, respectively), genes implicated in peptide processing and loading (*TAP1*, *TAP2*, *TAPBP*), and genes related to interferon- γ , which is known to upregulate MHC class I, including *JAK1/2*, interferon- γ receptor 1/2 (*IFNGR1/2*), interferon regulatory factor 1 (*IRF1*), suppressor of cytokine signaling 1 (*SOCS1*), and protein inhibitor of activated STAT4 (*PIAS4*).^{59,110}

WES and RNAseq analyses will also investigate the association between immune pathways and response. WES data will be analyzed to calculate tumor mutation burden, which is associated with response to immunotherapy in other tumors.¹⁰⁸ HLA genotypes will be assessed with OptiType, an integer linear programming algorithm that predicts HLA genotype with an overall accuracy of 97%.¹¹¹ Neoantigen prediction will be accomplished with NetMHCpan, a method that utilizes both binding affinity and antigen processing data obtained from mass spectrometry.¹¹¹

Similarly, RNAseq data will be analyzed to estimate immune cell subpopulations and overall immune cell infiltrate with the digital cytometry method CIBERSORTx.¹¹² The cytolytic activity of the local immune cell infiltrate will be calculated as the geometric mean of *PRF1* and *GZMA* expression,¹¹³ and gene set enrichment analysis will be performed using canonical molecular signatures,¹¹⁴ such as the Hallmark gene sets,¹¹⁵ as well as a carefully curated compendium of immune signatures.¹¹⁶ Existing transcriptional signatures reported to be associated with response to immunotherapy, such as interferon- γ and T cell effector signatures,^{110,117} will be assessed in the subset of patients treated with pembrolizumab. As bulk RNAseq only detects T cell receptors

(TCR) on the most abundant T cells at a rate close to 1 TCR per 10 million reads,¹¹⁸ we will consider target specific TCR sequencing methods, which capture greater TCR diversity.¹¹⁹

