The T-cell inflamed phenotype has positive prognostic value for several types of cancer, including breast cancer,^{49,50} suggesting that an attempt by the host to generate an anti-tumor immune response reflects a biologic process associated with improved clinical outcomes.⁴⁷ In breast oncology, different groups have demonstrated that the amount of tumor infiltrating lymphocytes (TILs) in a tumor specimen, commonly assessed by histological evaluation of a standard hematoxylin and eosin-stained slide by a trained pathologist, is a significant predictor of both response to therapy and overall disease outcomes in the neoadjuvant and adjuvant settings.⁵¹⁻⁵⁷ Recently, more in-depth methods of immunologic profiling have been explored in breast cancer, for example, mRNA expression of immune-activating and immunosuppressive factors, and these additional immune profiles also appear to have prognostic significance.⁴⁹ Furthermore, in the metastatic setting, the T-cell-inflamed phenotype appears to be associated with clinical response

to several immunotherapies, including checkpoint blockade.⁵⁸ Thus, one of the main objectives of the correlative science in this trial is the characterization of a broad array of immune markers in HR+ / HER2- MBC to investigate whether these markers predict response to immunotherapy.

Considering the mechanism of action of anti-PD-1/anti-PD-L1 drugs, the absence of significant T-cell infiltrate, in addition to low expression of immune checkpoint molecules, may correlate with a non-inflamed tumor phenotype that is associated with *de novo* resistance to these agents. For this group of patients, therapeutic strategies that promote an increase in cytotoxic T-cell infiltration, such as antibody-drug conjugates, may be crucial to successfully overcoming T-cell exclusion and improve the likelihood of benefit of PD-1 blockade.

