13.7 Correlative Endpoints

13.7.1 Tumor biopsies and TIL assessment

Previous studies have demonstrated that, in addition to direct cytotoxic effects, chemotherapy-induced cell death can be immunogenic, causing T cell tumor infiltration and sensitizing tumors to immune checkpoint blockade.⁹⁸ Cytotoxic CD8+ T cell infiltration has been reported to increase after treatment with chemotherapy across different tumor types.⁹⁹⁻¹⁰¹ Recently, Herbst et al.

demonstrated that patients who had an increase of at least 5% in expression of PD-L1 in the tumor microenvironment were more likely to respond to the PD-L1 inhibitor atezolizumab.⁵⁸ Modifications in molecular signatures of the tumor microenvironment also correlated with response to therapy.

Tumor-infiltrating lymphocytes (TILs) by histological assessment will be quantitative and evaluated as a percentage of cells stained (0-100%). Data from Loi and colleagues suggest that the mean number of TILs in first-line HR+ / HER2- MBC is likely similar to that observed in first-line metastatic HER2-positive samples from the CLEOPATRA study.¹⁰² The median TIL value was 10% with a mean number of TILs of 17% (standard deviation as a continuous variable of 21%). TILs will be analyzed as a continuous variable using descriptive statistics to summarize the distribution observed among study participants.

A) To assess the relationship between baseline TILs and progression-free survival, we plan to perform a mandatory research biopsy of a safely accessible tumor lesion at baseline. The association of TILs and PFS will be evaluated in a proportional hazards regression model with treatment effect and study stratification factors as covariates.¹⁰³ Linear and non-linear components of the model will be assessed using Wald-type tests. If a non-linear association is detected, the point estimate and 95% prediction bands will be reported for the log relative hazard over the entire distribution of TILs. If no significant non-linear effects are observed, the step-down model will evaluate the linear multivariate proportional hazards regression model and report the adjusted hazard ratio and 95% confidence interval for a linear increase in TILs. In addition, modification of the treatment effect will be explored as an interaction test, and if non-significant (two-sided alpha = 0.05), the step-down model with main effects will be reported.

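### The published immunotherapy-response signatures are assigned to pembrolizumab-treated patients with no stated Arm B analysis, so for them prognostic and predictive value cannot be told apart

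*Combined protocol and SAP*

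**What the plan says.** Section 13.7.2 takes a set of signatures from the literature, "Existing transcriptional signatures reported to be associated with response to immunotherapy", gives interferon-gamma and T-cell effector signatures as examples, and states that they "will be assessed in the subset of patients treated with pembrolizumab". No other section assigns these signatures to Arm B.

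The governing objective, in Section 1.4.1, is to explore tissue biomarkers "as predictors of response and resistance to sacituzumab govitecan plus pembrolizumab compared to sacituzumab govitecan alone". One sub-aim under it is "To characterize RNA expression signatures of immune pathway activation and DNA damage repair deficiency at baseline and correlate with disease response to treatment" (PFS, ORR and OS), with no restriction to one arm.

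Section 2.6.1 gives the biological background: "The T-cell inflamed phenotype has positive prognostic value for several types of cancer, including breast cancer".

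Three other parts of the plan bear on the point:

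- Section 13.7.2 also states "We will compare genomic and transcriptomic markers between responders and non-responders". This covers interferon-gamma signaling and T-cell effector pathways, and it is followed by immune-cell deconvolution, a cytolytic score and gene set enrichment. None of these is limited by arm, and none names an arm term or an interaction.
- Section 13.7.1 plans, for TILs and PFS, that "modification of the treatment effect will be explored as an interaction test". The same section analyzes Trop-2 by treatment group, and Section 9.6.3 compares microbiome associations between the two regimens.
- Section 9 makes all blood and tissue biomarker analyses exploratory.

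**The concern.** The objective is comparative, but the analysis set named for these signatures has no comparator. Under Section 5.7, Arm B patients receive sacituzumab govitecan only, including at retreatment, so the pembrolizumab-treated subset excludes Arm B entirely. It is also an as-treated set: an Arm A patient who started sacituzumab govitecan but never received pembrolizumab would drop out, although that patient stays in the modified ITT population of Section 13.8.1.

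Within one arm, a signature that marks better outcome under any treatment looks the same as one that marks benefit from pembrolizumab. The protocol's own background makes the first explanation plausible, because these signatures measure biology close to the T-cell-inflamed phenotype. What is at stake is how an exploratory result is read, and whether later biomarker work would start from a signature that says nothing specific about pembrolizumab. The primary PFS comparison, the secondary endpoints and the safety analyses are not affected.

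**Working it through.** The plan states no sample size, power or alpha for this analysis, so there is no figure to reproduce. The check sets objective against analysis set and then illustrates the size.

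**Step 1. Objective against analysis set.**

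| Item | Section | Arms covered |
|---|---|---|
| Objective for tissue biomarkers | 1.4.1 | Combination compared with monotherapy |
| Published immunotherapy signatures | 13.7.2 | Pembrolizumab-treated only |
| Responder comparison, pathway, enrichment and cytolytic analyses | 13.7.2 | Not restricted; no arm term |
| TILs and PFS | 13.7.1 | Both, with interaction test |
| Trop-2 | 13.7.1 | By treatment group |
| Microbiome | 9.6.3 | Between regimens |

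The row for the published signatures is the only one confined to a single arm.

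**Step 2. How often an Arm A test would pick up a purely prognostic signature (response).**

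Inputs:
- 55 patients per arm (Section 13.1) as the upper limit for evaluable RNA.
- 24 per arm as a lower illustration, borrowed from the paired-sample count in Section 13.7.1.
- Response rate from 31.5% (Section 2.4.5, HR+ cohort) to 35% (assumed).
- Odds ratio per SD of 1.5 or 2.0, the same in both arms (assumed; not in the documents).

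Model: score x ~ N(0,1), logit P(response) = a + ln(OR)·x, with a set to give the response rate. Test: two-sided Wald at 0.05, without multiplicity adjustment. Simulated proportion significant in Arm A alone, with simulation error of a percentage point or two:

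| Evaluable per arm | OR 2.0 | OR 1.5 |
|---|---|---|
| 55 | 58–59% | 24–27% |
| 35 | 35–39% | 15–16% |
| 24 | 21–22% | 9% |

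These figures are power for an association that truly exists in Arm A. They are not false-positive rates.

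**Step 3. The same for PFS.**

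Assume a median-split signature, all patients assayed, and 40 to 50 PFS events per arm. The upper value is the 100 events of Section 13.2 split evenly. The lower value is an assumption, since Section 13.2.1 says 100 will not be reached. One-arm power is Φ(|ln HR|·√e/2 − 1.96). For a prognostic HR of 0.50:

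- e = 50: 0.693 × 7.071/2 = 2.451; Φ(0.491) = 0.69
- e = 40: 0.693 × 6.325/2 = 2.192; Φ(0.232) = 0.59

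For HR 0.65 the range is 0.28 to 0.33, and for HR 0.40 it is 0.83 to 0.90.

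**Step 4. What a score-by-arm term could detect.**

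- Response, with OR 2.0 in Arm A and 1.0 in Arm B (assumed): power about 33% with 55 per arm and about 15% with 24 per arm.
- PFS, with SE of the log ratio of hazard ratios = √(4/e + 4/e). At e = 50 the SE is 0.40. For a ratio of 0.50, 0.693/0.40 = 1.733 and Φ(1.733 − 1.96) = 0.41. At e = 40 the SE is 0.447 and power is 0.34. For a ratio of 0.65, power is 0.16 to 0.19.

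**The case against.** The strongest case on the other side has five parts.

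1. *The restriction sits on one sentence.* The same section studies interferon-gamma signaling, T-cell effector pathways, cytolytic activity and immune gene sets without restriction by arm. Objective 1.4.1 is a heading over many sub-aims, and comparative analyses are planned for TILs, Trop-2 and the microbiome. This stands. A reader might infer that objective 1.4.1 goes unanswered; the documents do not support that. What remains is that the unrestricted analyses in 13.7.2 name no arm term, so they fill the gap only in part.

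2. *The text does not say that Arm B is barred.* True, but naming a subset defines the analysis set, and no Arm B assessment of these signatures is stated.

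3. *Arm B RNA is not assured.* A reader might infer that a complete comparator data set is in hand and being discarded. The documents do not show this. Biopsies depend on safely accessible tumor; bone-only disease is eligible, yet bone and lung lesions are not biopsied unless clinically indicated (Sections 3.1 and 9.2.2); and RNA analysis is described as something that may be performed (Section 9.3.3). The same collection rules apply to both arms, so some Arm B material should be available, but its amount is unknown.

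4. *The simulated percentages can mislead.* A reader might set the top value of 59% beside the 5% error rate of an interaction test and read the first as a false-positive rate. That would be wrong. The 59% is power for a real association, under an assumed odds ratio and full assay yield, while the 5% is the type I error of a different test, fixed by construction.

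5. *Checking published immunotherapy signatures in treated patients is a legitimate descriptive step, and the work is exploratory.* Both are correct. The Arm A result can stay, reported as descriptive.

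**Conclusion.** The point holds in a limited form. For the published interferon-gamma and T-cell effector signatures, the analysis set named in Section 13.7.2 cannot separate prognostic from predictive value, while Section 1.4.1 asks for a comparison with sacituzumab govitecan alone. This follows from the text and needs no assumption.

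The size does rest on assumptions. With a purely prognostic odds ratio of 1.5 to 2.0 per SD and 24 to 55 evaluable patients per arm, an Arm A test would be significant in roughly 9% to 59% of trials. Section 13.7.2 does not itself call such a result predictive; the harm arises only if a reader does.

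Importance is low. The analysis is exploratory, covers one group of signatures and touches no primary, secondary or safety conclusion. It is an optional improvement, worth making because it is cheap and brings these signatures into line with the approach already planned for TILs.

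**What to change.** Change the sentence in Section 13.7.2 so that:

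- the published signatures are scored in all patients with evaluable RNA in both arms, analyzed as randomized;
- each outcome has one model with arm, continuous signature score and score-by-arm (logistic for ORR, Cox for PFS and OS);
- the score association is reported within each arm with a confidence interval and the number evaluable, the Arm A result being labeled descriptive;
- the Benjamini-Hochberg control already named in Section 13.7.2 is applied to this set of tests, and the analysis stays exploratory.

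The cost is SAP wording, RNA assays on whatever Arm B tissue is available, where not already run, and modest analysis time; no new sample collection is needed. The drawback is imprecision. With the interaction power shown in the working (about 33% at 55 per arm and 15% at 24 per arm for an odds ratio of 2.0 against 1.0), a null interaction would not rule out a predictive effect. The text should say so and put the weight on estimates and intervals, not on the test.
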